5.4 HEALTHCARE UTILIZATION

Healthcare service utilization will be assessed via participant reports. At Day 1 and at each subsequent assessment, participants will be asked to indicate the number of all-cause and (separately) mental health-related encounters or visits they had for themselves in the previous month/4 weeks within the following categories of service: inpatient (hospital), emergency department, and outpatient medical; outpatient psychotherapy and psychotropic prescription utilization will also be assessed. Additionally, participants will be asked at each assessment (Weeks 4 and 8) to report the healthcare service utilization (i.e., inpatient/hospital, emergency department, and outpatient services) of their new babies during the previous month/4 weeks.

5.5 BLINDING ASSESSMENT

The success of maintaining the participant blind will be evaluated by the 'Program Assignment Assessment'. This two question patient reported scale will be administered at Week 8 and ask participants to select the treatment group which they believe they were assigned to (see additional details in the SAP).

6. STUDY STOPPING RULES

Study procedures will be stopped if the Sponsor in discussion with the DSMB, IRB, and/or investigator(s), as applicable, determines that the number and/or severity of AEs or abnormal safety monitoring tests justify putting the study on hold. See Section [7.4](#) Data Safety Monitoring Board (DSMB).

The investigator may initiate study-site closure at any time, provided there is reasonable cause and sufficient notice is given in advance of the intended termination.

The study may resume following the safety review, if the PI and Sponsor agree it is safe to proceed.

Study sites will be closed upon study completion. A study site is considered closed when all required documents and study supplies have been collected and a study-site closure visit has been performed.

6.1 EARLY STUDY TERMINATION

The study can be terminated by the Sponsor at any time. Reasons for early termination include:

- Study recruitment or retention is too low for the study to provide meaningful results
- Unanticipated, significant, or unacceptable safety risk to participants enrolled in the study

Sponsor Name: Woebot Health

Protocol Number: WB001-001

- Decision based on recommendations from PI and DSMB after review of safety and efficacy data
- Discontinuation of study if PIs, in collaboration with study clinicians and DSMB, determine from planned analyses that the app is not efficacious or if there are safety concerns.

In taking the decision to terminate, the Sponsor and DSMB will always consider the participants' welfare and safety. Should early termination be necessary, participants must be seen as soon as possible to conduct a formal assessment and treated as a prematurely withdrawn participant. The investigator may be informed of additional procedures to be followed to ensure that adequate consideration is given to the protection of the participant's interests. The investigator or Sponsor depending on the local regulation will be responsible for informing Institutional Review Boards (IRB) of the early termination of the trial.

7. DATA AND SAFETY MONITORING

Data monitoring will be conducted by the research coordinator and site staff (research team) and overseen by project PIs.

During data collection and monitoring, study coordinators will follow an internal safety protocol and alert a study PI of any clinical concerns. A clinical concern is defined here as any negative experience or symptom that occurs during baseline or post randomization sessions that are raised via email/text/phone correspondence directly by the patient, or in key assessment visits to the CIR, whether it is associated with participation in the study.

The PIs in consultation with study site staff will be responsible for monitoring participant safety during the study and will review relevant data/information to determine whether it is appropriate for the participant to continue study participation and whether further action to ensure the safety and wellbeing of the participant is warranted.

Given this study will be conducted among women with PPD, there are clinical concerns that may be anticipated in the target patient population due to the natural course of disease. Anticipated clinical concerns may include suicidal ideation, clinically significant deterioration in depressive symptoms, self-injurious behavior, suicide attempts, and completed suicide. These events will be recorded and will be elevated to AE or SAE status if deemed appropriate by the investigator, and promptly reported to the Sponsor. As part of a Safety Monitoring process, all AEs/SAEs will require DSMB review, and the Sponsor can query any PI-determined AEs/SAEs.

TABLE 3 CLINICAL CONCERN CATEGORIZATIONS

Clinical Concern	Definition
0 - Not a clinical concern:	Qualified research personnel determined that triggering event was not a clinical concern

Sponsor Name: Woebot Health

Protocol Number: WB001-001

1- Mild clinical concern:	Qualified research personnel determined that triggering event doesn't require investigator input and will continue to monitor participant's responses
2- Moderate clinical concern:	Qualified research personnel determined that triggering event requires investigator input. PI/Clinician determined that the research team should continue to monitor participant's responses but that no follow-up was needed.
3- Elevated clinical concern:	Qualified research personnel determined that triggering event requires clinician input. PI/Clinician determined follow-up was indicated and confirmed participant safety (participant did not endorse intent to self-harm) via email or phone communication with participant or their provider.
4- Significant clinical concern:	Qualified research personnel determined that triggering event requires clinician input. PI/Clinician determined that follow-up was indicated and after follow-up with participant, parent/guardian, or provider determined that participant should be withdrawn from study (e.g., due to suicide attempt, self-harm or self-harm attempt, suicidal ideation with intent, reported hospitalization for self-harm or suicide attempt while enrolled in study).

All clinical concerns documented as level 4 of concern will be reported to the DSMB for review and oversight within 5 working days to ensure patient safety and efficient monitoring. In addition, appropriate reporting will be done to notify the Sponsor and IRB per details in Section [10.2](#) Institutional Review Board.

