SUICIDAL IDEATION AND BEHAVIOR RISK MONITORING

[figure not shown]
Sponsor Name: Woebot Health

Protocol Number: WB001-001

The study design includes assessment of suicidal ideation as described. All participants will meet with the investigator or qualified site staff at Baseline, Week 4, and Week 8 during a telehealth visit, and will be administered psychometric tests (i.e., C-SSRS and HAM-D item #3) to assess suicidal ideation.

C-SSRS

The clinician-administered C-SSRS is a measure used to identify and assess individuals at risk for suicide (The Columbia Lighthouse Project/Center for Suicide Risk Assessment, 2019). The C-SSRS measures four constructs: the severity of ideation, the intensity of ideation, behavior, and lethality. The C-SSRS is made up of ten categories, with binary responses (Yes or No) to indicate presence or absence of the behavior, and the outcome is a numerical score obtained from these categories. The C-SSRS will be administered by the investigator or qualified site staff during telehealth visits at baseline, Week 4, and Week 8 to monitor for potential onset of suicidal ideation. If a score on the C-SSRS raises a safety concern, i.e., 'yes' on questions 4 or 5, or answer 'yes' to "actual attempt" question in "Suicidal Behavior" section the site-based rater will immediately contact the PI/sub-investigator to ensure that the investigator urgently conducts an assessment of this participant to determine the appropriate actions to take and disposition of the participant. Similarly, if a safety concern is raised due to a score submitted through a CIR administered structured clinical interview (a score of ≥ 2 on the HAM-D17 item #3) or self-report ePROs (a score of ≥ 2 on item #9 of PHQ-9 and/or score of > 2 on item #10 of EPDS), an electronic system at the sites will notify the investigator to review each incident and follow up with the participant within 24 hours to determine if any action is required. If so, the investigator will be responsible for administering a formal assessment using the C-SSRS, if deemed necessary.

Sponsor Name: Woebot Health

Protocol Number: WB001-001

[REDACTED]

[REDACTED]

[REDACTED]

[REDACTED]

[REDACTED]

[REDACTED]

PREGNANCY AND BREASTFEEDING

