7.4 DATA SAFETY MONITORING BOARD (DSMB)

The Data Safety Monitoring Board is co-responsible for the oversight and safety monitoring of the study. The DSMB advises the Sponsor regarding the continuing safety of the trial participants and those yet to be recruited to the trial, as well as the continuing validity and scientific merit of the trial. The team assembled for the DSMB will have relevant and complementary expertise in psychiatry, obstetrics and gynecology, clinical trial design, digital health, and statistics. This DSMB should include members from academic sites independent of the study sites and should consist of at least one non-study, board-certified psychiatrist and one biostatistician.

Sponsor Name: Woebot Health

Protocol Number: WB001-001

Importantly, none of these individuals will be involved in any other capacity with this study or have any potential conflicts of interest in study-related outcomes.

The DSMB will review and evaluate information relevant to the safety of this study before the implementation of the protocol. Activities of the DSMB will include:

1. Developing the DSMB Charter that will be approved by the Sponsor (including study stopping criteria and final interim analyses being conducted by the independent statistician etc.)
2. Reviewing the study protocol at the start of the study and any proposed amendments related to changes in study design, safety monitoring, or analytic plan
3. Recommending alterations to the study design
4. Approving the study protocol before commencement
5. Performing expedited monitoring of unanticipated serious adverse device effects at the time of their occurrence and providing recommendations accordingly
6. Performing quarterly review of all clinical concerns
7. Performing ongoing quarterly review of study progress
8. Reviewing any data that may reflect differences in safety between treatment groups
9. Determining whether study procedures should be changed, or the study should be halted for reasons related to the safety of study participants
10. Performing quarterly review of the completeness and validity of data to be used for analysis of safety and efficacy.

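### Table 3 ties the 5-working-day DSMB report to the decision to withdraw the participant, not to the event, so serious self-harm concerns in women who are kept in, or whom nobody can reach, miss that clock

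*Combined protocol and SAP*

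**What the plan says.** Table 3 in Section 7 grades clinical concerns from 0 to 4. Level 2 applies where the investigator's input was needed but follow-up was not. Levels 3 and 4 both start from a judgement that follow-up was indicated:

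- **Level 3** also requires that the PI or clinician "confirmed participant safety (participant did not endorse intent to self-harm) via email or phone communication with participant or their provider".
- **Level 4** also requires that, "after follow-up with participant, parent/guardian, or provider", the PI or clinician "determined that participant should be withdrawn from study (e.g., due to suicide attempt, self-harm or self-harm attempt, suicidal ideation with intent". A reported hospitalization for self-harm or attempt is a further example in the same bracket.

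The sentence below the table sets the clock: "All clinical concerns documented as level 4 of concern will be reported to the DSMB for review and oversight within 5 working days". No other level carries a stated time.

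Withdrawal is a judgement. After a C-SSRS safety flag, Section 5.3 has the investigator assess the participant urgently "to determine the appropriate actions to take and disposition of the participant". Section 7 likewise leaves continued participation to the PIs in consultation with site staff. It lists suicidal ideation, self-injury, attempts and completed suicide as anticipated concerns, to be "elevated to AE or SAE status if deemed appropriate by the investigator". For concerns as such, the DSMB's listed task in Section 7.4 is "Performing quarterly review of all clinical concerns".

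Section 4.6 says that when a participant withdraws or is withdrawn, the sponsor, the sites and the DSMB are told immediately.

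**The concern.** A rule for fast notice to a safety board should be triggered by what happened. Here it is triggered by what the site decided to do about it. Two women with the same event can be recorded at different levels, or one of them at none, because one was withdrawn and the other was not.

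The 5-day rule also adds least where it applies. A woman who is withdrawn is already covered by the immediate notice in Section 4.6. A woman who stays in, and keeps using the assigned app, has neither notice. She is the participant for whom prompt independent review is most useful, because her exposure continues.

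**Working it through.** No power, alpha or sample size figure enters, and the plan states no number to reproduce. The check takes the outcomes that can follow once follow-up is indicated and gives each the level that Table 3 literally assigns.

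| | Contact | Finding at follow-up | Disposition | Table 3 level | 5-day DSMB report |
|---|---|---|---|---|---|
| a | made | intent endorsed | withdrawn | 4 | yes |
| b | made | intent endorsed | kept in | none | no |
| c | made | safety confirmed, no intent endorsed | kept in | 3 | no |
| d | made | safety confirmed, no intent endorsed | withdrawn | fits both 3 and 4 | only if recorded as 4 |
| e | nobody reached | not known | not decided | none | no |

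- **Outcome b.** Level 2 fails because follow-up was needed, level 3 because intent was endorsed, and level 4 because she was not withdrawn.
- **Outcome c.** Level 3 applies even if the triggering event was an attempt or self-harm.
- **Outcome e.** Level 3 presupposes contact with the participant or her provider; level 4 presupposes contact with her, a parent or guardian, or her provider. Only when all of these fail is there no level. The lost-to-follow-up rule in Section 4.7 does not close the gap, because it needs both key visits to be missed. A woman flagged at her Week 4 visit who then goes silent has missed at most one.

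Two of the five outcomes (b, e) have no level. Three of the five (b, c, e) fall outside the 5-day report, whatever the triggering event was.

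The other routes to the DSMB are these:

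1. **All AEs and SAEs (Section 7).** DSMB review is required, with no deadline. The event must first be elevated at the investigator's discretion. Section 7.1 defines an AE as an unanticipated occurrence, while Section 7 calls these events anticipated, which gives a reason not to elevate.
2. **Serious or related AEs (Section 7.3).** They go to the DSMB on an ongoing basis, with details left to the charter. Under Section 7.2 an event reasonably explained by the disease under study is unrelated. Ideation with intent but without hospitalization is not named among the SAE criteria and would have to be judged an important medical event.
3. **SAE report within 24 hours (Section 7.3).** It goes to the sponsor, not the DSMB.
4. **Expedited DSMB monitoring (Section 7.4, item 5).** It covers unanticipated serious adverse device effects.
5. **Quarterly review of concerns (Section 7.4, item 6).** A quarter is 52 / 4 = 13 weeks, against 8 weeks of participation.

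Section 4.6 adds two conflicts. Item 3 cites Table 3 for SAEs of Grade 3 (severe) or higher, but Table 3 contains concern levels and no SAE grades. Its level 3 means safety confirmed; the severity grades are in Section 7.2. And Section 4.6 sets immediate DSMB notice on withdrawal, while Section 7 allows 5 working days for level 4, which exists only where withdrawal has been determined.

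**The case against.** The strongest reply is that most serious events reach the DSMB anyway. An attempt rated as an SAE of Grade 3 or higher meets a discontinuation criterion in Section 4.6, so it should become level 4, and the DSMB is then told at once. Serious AEs go to the DSMB on an ongoing basis, all AEs and SAEs require its review, and the sponsor may query the PI's determinations. The Table 3 bracket can also be read as a list of events for which withdrawal is expected. Redacted text in Section 5.3 and Appendix 3, the DSMB charter and the internal safety protocol may deal with retained or unreachable women.

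Much of this stands, and it limits the point. It does not remove it, because SAE status and grade rest on the investigator's judgement, and Section 5.3 leaves disposition open after the same events. The defect lies in Table 3 and the sentence below it, both of which are fully visible.

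A reader might infer more than the documents support:

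- **That every attempt in a woman kept in has no level.** It is level 3 if safety is confirmed and no intent is endorsed.
- **That failing to reach the participant alone leaves no level.** Contact with her provider can support level 3 or 4, and with a parent or guardian level 4.
- **That a completed suicide would go unreported.** No level describes it, but death is an SAE criterion in Section 7.3 and serious AEs go to the DSMB.
- **That the planned safety comparison is distorted.** The safety endpoints are the C-SSRS, AEs and SAEs; no analysis of concern levels by arm is planned.

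**Conclusion.** The point holds as a defect in a stated reporting rule. The 5-working-day DSMB report depends on the withdrawal decision, and three of five outcomes after follow-up fall outside it. What is lost is the fixed clock, not all DSMB review. If an event is not elevated to an AE or SAE, the only interval left in the protocol is quarterly. Thirteen weeks is therefore an upper bound, reached only when the event falls just after a review and no other route picks it up.

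The number of women affected cannot be given, since the documents state no rate for these events and no share kept in or unreached. The conclusion rests on a literal reading of Table 3 and on the charter and redacted text not already closing the gap. It has no bearing on the primary efficacy analysis, and no view is taken on who should be withdrawn.

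**What to change.** Tie the 5-working-day DSMB report to the events already listed in the level 4 row, whether or not the participant is withdrawn. Record disposition (withdrawn or kept in) in a separate field. Send cases where safety could not be confirmed, including those where nobody was reached, by the same route.

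Then reconcile Table 3 with three other places: Section 4.6, on the Grade 3 cross-reference and on immediate notice against 5 working days; Section 5.3, on disposition after a C-SSRS flag; and Section 7.2, on the severity grades. Which events lead to withdrawal is for the sponsor to settle there.

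The cost is a rewording of the level 3 and 4 rows and the sentence below the table, one extra field on the concern log, and a few more expedited DSMB notices.

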7.1 ADVERSE EVENTS

An AE is any unanticipated medical occurrence in a participant or clinical study participant using an investigational product that does not necessarily have a causal relationship with this product. An AE can therefore be any unfavorable and unintended sign (including an abnormal laboratory finding), symptom, or disease temporally associated with the use of an investigational product, whether or not related to the investigational product.

All AEs recorded during the study period will be assessed for: severity grade (mild, moderate, severe, fatal/life-threatening, relationship to the study treatment or conduct, duration, and whether it is deemed an SAE as defined by Sponsor and requires an action taken regarding study treatment to avoid a negative outcome(s).

Sponsor Name: Woebot Health

Protocol Number: WB001-001

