5.3 SAFETY ASSESSMENTS

To further manage risk in this clinical trial of WB001, the study will incorporate validated psychometric assessments conducted at regular intervals to monitor for worsening symptoms and/or the development of suicidal ideation. The study population will only include participants with mild-moderate depression (inclusion

Sponsor Name: Woebot Health

Protocol Number: WB001-001

criterion) and specifically excludes patients with severe depression and prior history of treatment-resistant depression (exclusion criteria). The study will also appropriately monitor worsening of symptoms through the following:

- a. Administering the C-SSRS at BL, Week 4, and Week 8
- b. Administering the PHQ-9 (item #9), EPDS (item #10), and HAM-D (item #3) at BL, Week 4, and Week 8
- c. This protocol continues to adhere to FDA guidance that appropriate assessments, such as assessing for AE/SAEs and administering the C-SSRS, should occur at each planned visit wherein the other clinical assessment will be administered. Thus, the assessment schedule for the C-SSRS mirrors that of the HAM-D.
- d. Study participants are welcome to initiate contact anytime throughout the duration of the study with their site. If the contact is attributable to safety reasons, then an Unplanned Visit would ensue, wherein qualified study personnel would follow-up with the participant in a timely manner, and if needed administer the C-SSRS.

Scenarios that would trigger an escalation for an Unplanned Visit include:

- [REDACTED]
- [REDACTED]
- [REDACTED]

ADVERSE EVENTS

At each telehealth visit, the PI and site staff will evaluate participants for any changes that could indicate AEs. Participants with AEs will be followed, recorded in the EDC and reported in line with the procedures described in Section 7. Participants will be instructed to contact the study site if any new symptoms occur in between the weeks of telehealth visits. The CIR is responsible for detecting, documenting, and recording any potential safety events based on the administered HAM-D (i.e., score of ≥ 2 on HAM-D17 item #3) that may meet the definition of an AE or SAE, but the investigator will remain responsible for following up on all safety events to confirm if an AE/SAE has occurred and determine the appropriate course of action. The method of recording, evaluating, and assessing causality of AEs and SAEs and the procedures for completing and transmitting SAE reports are provided in Section 7.

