7.3 SERIOUS ADVERSE EVENTS

An SAE is any AE that meets any of the following criteria:

- Results in death
- Is *life-threatening*
- Requires inpatient *hospitalization* or prolongation of existing hospitalization
- Results in persistent or significant *disability/incapacity*
- Is an *important medical event*

Sponsor Name: Woebot Health

Protocol Number: WB001-001

UNANTICIPATED ADVERSE DEVICE EFFECTS

A suspected unanticipated adverse device effect (UADE) is defined as an untoward and unintended response to a study treatment, which is not listed in the applicable product information, and meets at least one AE or SAE criterion, and is assessed as causally related to the study treatment. The Sponsor or designee will be responsible for carrying out required reporting to investigators, health authorities, and other entities as required by law.

DOCUMENTING AND REPORTING ADVERSE EVENTS AND SERIOUS ADVERSE EVENTS

Reporting of non-serious AEs and SAEs will begin at the time of first interaction with the app and will continue through EOT. Any new clinical condition or worsening of existing conditions between the time the informed consent form (ICF) is signed, and the first use of the study intervention will be recorded as AE/SAEs unrelated to the device.

AEs and SAEs may be reported spontaneously by participants, discovered as a result of general, non-leading verbal questioning by the study staff, or determined by assessments. As needed, qualified study staff will inform investigators to inquire about any new symptoms or worsening of symptoms during the telehealth visits at Weeks 4 and 8. In the interim, participants will be instructed to contact the investigator if new or worsening symptoms develop outside of key assessment visits. All incidences confirmed as AEs or SAEs will be monitored and recorded in the eCRF throughout the entire study.

The investigator must pursue and obtain adequate information about all incidences they deem as AEs and SAEs. At minimum this includes a description of the event, severity, device relatedness, start and stop times, duration, outcome, and any action (e.g., treatment/follow-up tests). The investigator must also assess whether the event meets the criteria for classification as an SAE.

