9.4 SAFETY ENDPOINT(S)

AEs and SAEs that may be reported by the participant or detected by the investigator through the C-SSRS will be compared between treatment groups. All safety variables will be summarized descriptively by randomized treatment.

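### Section 7.1 defines an AE as unanticipated, while section 7 calls suicidality and worsening depression anticipated, so a literal reading can leave these events out of the AE/SAE comparison

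*Combined protocol and SAP*

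**What the plan says.** Section 7.1 begins: "An AE is any unanticipated medical occurrence in a participant or clinical study participant". Its next sentence is wider and carries no such limit: "An AE can therefore be any unfavorable and unintended sign (including an abnormal laboratory finding), symptom, or disease temporally associated with the use".

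Section 7 describes what is expected from the natural course of the disease: "Anticipated clinical concerns may include suicidal ideation, clinically significant deterioration in depressive symptoms, self-injurious behavior, suicide attempts, and completed suicide". On their classification it says: "These events will be recorded and will be elevated to AE or SAE status if deemed appropriate by the investigator".

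Section 7.3 then builds seriousness on AE status: "An SAE is any AE that meets any of the following criteria". For events picked up by the central rater, section 5.3 says the rater detects and records them, "but the investigator will remain responsible for following up on all safety events to confirm if an AE/SAE has occurred".

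Section 9.4 sets the comparison: "AEs and SAEs that may be reported by the participant or detected by the investigator through the C-SSRS will be compared between treatment groups". It adds that all safety variables are summarised descriptively by randomised arm.

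**The concern.** The harms that matter most in a trial of women with postpartum depression are labelled anticipated, and the AE definition opens by restricting AEs to what is unanticipated. Read together and literally, a suicide attempt need not be an AE. If it is not an AE, it cannot be an SAE. Whether it becomes one is left to each investigator, with no stated criterion, at up to 25 centres.

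Four things depend on AE or SAE status: the between-arm comparison in 9.4, the MedDRA frequency tables and listings in 9.5, the 24-hour report to the Sponsor in 7.3, and the limb of the section 6 hold rule that refers to the number and severity of AEs. An event left as a clinical concern reaches none of these by right.

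**Working it through.** No sample size, power or rate enters this point, so the check is a comparison of the texts.

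**1. The route to exclusion.** Section 7.1, first sentence: an AE is unanticipated. Section 7: the five listed event types are anticipated, and AE or SAE status follows only from the investigator's judgement. Section 7.3: an SAE is a kind of AE. Sections 9.4 and 9.5: what is compared and tabulated is AEs and SAEs. Each step is in the text, and together they allow a listed event to stay outside the safety endpoint.

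**2. Text that conflicts with this route.**
- The second sentence of 7.1 covers unfavourable, unintended symptoms whether or not they were foreseen.
- Section 7.2 reports an event explained by the disease under study as unrelated. That presupposes that such an event is already an AE.
- The benefit/risk assessment in section 1 names worsening PPD symptoms as the main risk that could give rise to AEs.
- Section 7.3 records any new or worsening condition between consent and first app use as an AE or SAE, with no discretion clause. The rule is therefore looser after exposure starts than before it.
- The definition of an unanticipated adverse device effect in 7.3 already uses *untoward* and treats expectedness as a separate matter.

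The protocol is therefore inconsistent with itself. It does not state one clear exclusion.

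**3. What remains visible outside AE status.** Section 7 says the listed events are recorded. The synopsis makes the C-SSRS a safety endpoint in its own right, and 9.4 summarises it by arm. After Table 3, level 4 concerns go to the DSMB within 5 working days, with notice to the Sponsor and IRB. Under 7.4 the DSMB reviews all clinical concerns quarterly.

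**4. Where these backstops stop short.**
- Appendix 3 schedules the C-SSRS only at baseline, Week 4 and Week 8, and it cannot be given after a completed suicide.
- The Safety set in Table 4 requires a post-baseline C-SSRS. A suicide before any such assessment falls outside that set even when classified as an SAE.
- Level 4 in Table 3 turns on a decision to withdraw the participant, not on the event alone.
- Section 7 lets the Sponsor query AEs and SAEs that the investigator has determined. It states no equivalent check on concerns that were not elevated.
- No readable section provides a by-arm table of concerns that were not elevated.

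**5. Size and direction.** Let p_W and p_E be the true proportions with a listed event in the WB001 and ED001 arms, and f_W and f_E the fractions of those events elevated. The AE data then show f_W × p_W and f_E × p_E.
- If f_W = f_E = f, the observed difference is f × (p_W − p_E) and the observed ratio is p_W / p_E. For any f above 0 and up to 1, the absolute difference shrinks in proportion and the ratio does not move. At an assumed f of 0.5 the difference is halved.
- If f_W and f_E differ, the ratio is multiplied by f_W / f_E, which can be above or below 1.

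The documents give none of the four quantities, so no magnitude follows.

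**The case against.** The strongest reply is that the rest of the protocol plainly intends these events to reach the AE data, and that *unanticipated* in 7.1 is a slip. The synopsis uses the C-SSRS, PHQ-9 item 9, EPDS item 10 and HAM-D17 item 3 to help identify AEs and SAEs. Section 5.3 treats a rater's HAM-D item 3 flag as a possible AE or SAE. Section 9.4 compares events detected through the C-SSRS. Section 7 itself allows anticipated events to be elevated, which would be impossible if being anticipated disqualified them. Some judgement is also needed, because section 7 defines a clinical concern very broadly and Table 3 includes a level for no concern at all. Parts of the suicidality text in 5.3, the escalation triggers and some rows of Table 1 are blacked out, and the DSMB charter is not in the published text.

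Much of this stands. A reader might infer that the protocol excludes suicidality from the AE data, or that these events vanish from the trial. The documents support neither reading, as steps 2 and 3 of the working show. A reader might also infer that the safety comparison is biased toward no difference. That holds for the absolute difference if capture is equal in both arms. The ratio need not move, and investigators are blinded under Table 2.

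What does not stand is that intent cures the text. Site staff apply the definition as written. The second sentence of 7.1 is phrased as following from the first, and it leaves the discretion in section 7 untouched. Judgement over which concerns are AEs is reasonable, but here it is given no criterion.

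**Conclusion.** The point holds as an inconsistency of classification that should be corrected. Sections 7, 7.1 and 7.3, followed literally, can leave serious self-harm events outside the AE/SAE endpoint and the reporting and hold rules tied to it. Sections 7.1 (second sentence), 7.2 and the benefit/risk assessment say otherwise.

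All five listed event types are affected, but no size or direction can be given. The conclusion rests on the published text, and a mandatory recording rule in the redacted parts or the DSMB charter would weaken it. It does not require that every suicidal-ideation flag be an AE. That is one convention among several, and the C-SSRS already captures such flags.

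**What to change.** - In 7.1, replace *unanticipated* with *untoward*.
- In section 7, state that being anticipated for PPD does not exclude an event from AE or SAE status. Any listed event that meets the 7.1 definition is recorded as an AE, and any that meets a 7.3 criterion as an SAE.
- Handle explanation by the disease through causality under 7.2, and keep expectedness as a separate field.
- In 9.4 or 9.5, add a table by randomised arm of all recorded suicidality and self-harm events, whatever their classification. It should not be limited to participants with a post-baseline C-SSRS.

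The cost is protocol wording, site training and higher AE counts. The changes concern recording and reporting only and alter no clinical management.
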